1 will involve the initial assessments and visit 2 will involve the initial EEG. Visit 3 will involve final assessments and visit Child participants will be assessed using the following measures: 1) hearing screening at 25 decibels for the frequencies 1000, 2000 and 4000 hertz; 2) *Test of Nonverbal Intelligence* 3 (TONI-3; Brown, Sherbenou & Johnsen, 2009; 3) *Social Skills Improvement System SSIS* - Student form (Gresham & Elliot, 2008); and 4) *Test of Pragmatic Language* -2 (TOPL-2; Phelps-Terasaki & Phelps-Gunn, 2007; See Supporting Materials). All assessment procedures with each child in Visits 1 and 3 will be video recorded and analyzed using the observation of self-stimulating behaviors checklist (See Supporting Materials). Additionally, parent participants included in the study will assess their children using a standardize measure: 1) the *Social Skills Improvement System SSIS* - Parent form (Gresham & Elliot, 2008) and a non-standardized measure: 2) the *Questionnaire for Parents of Children with Autism Spectrum Disorders* ([name], 2013) (developed by the researcher to identify self-stimulating behaviors); to assess their children's social skills (See Supporting Materials). Both assessments will be administered at the beginning and end of the study. These assessments are expected to last 2 hours. The twenty-five self-stimulating behaviors identified as a concern for this study include: hand flapping, pulling or twisting ear, scratching, masturbating, shuffling or tapping feet, chewing clothes, picking or rubbing clothes, sucking finger, playing with hair, vocal noises, mouthing, self-injurious behaviors, head banging , rhythmic rocking, twirling objects, tongue rolling and clicking, teeth clicking, head shaking, knocking knees together, gazing at a particular object, repetitive rubbing of mouth and face, finger manipulations, locking hands behind head, grimacing , and tensing whole body and shaking.

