The null hypothesis predicts that there will be no significant change in parent perceptions of self-stimulating behaviors or social skills following the *ProFoveate*™ intervention. The alternative hypothesis predicts that the *ProFoveate*™ intervention will have a significant effect on parent perceptions of self-stimulating behaviors and social skills behaviors. Regarding the electrophysiological measure (ERP) of change in neural activation, the null hypothesis states that following *ProFoveate*™ intervention, there will be no measurable change in ERP measures during an accepted cognitive task. The alternative hypothesis states that there will be a measurable difference in neural activation as demonstrated by changes in P50 and P300 peak and latency measures in the ASD group receiving *ProFoveate*™ intervention.

Inclusion/Exclusion Criteria

TITLE: The Effects of *ProFoveate™* on Reducing Self- Stimulating Behaviors In Children Diagnosed With Autism Spectrum Disorders.

PI: [name]

Co-I: [name]

A total of 30 parents and their children with ASD between the ages of 10-17 years will be recruited for this study. Participants who return consent and assent forms, must meet the following criteria to be included in the study:

Inclusion Criteria

- Have a documented diagnosis of high functioning autism spectrum disorders (autism, Asperger's syndrome, or PDD-NOS) as reported by specialists who use the established criteria (American Psychiatric Association,2000)
- Pass a hearing screening at 25 decibels for the frequencies 1000, 2000 and 4000 hertz
- Score 85 or above on the *Test of Nonverbal Intelligence- 4* (TONI-4; Brown, Sherbenou & Johnsen, 2009)
- Exhibit noticeable self- stimulating or ritualistic behaviors (i.e., scratching, hand flapping, eye blinks, etc.) and/or visual characteristics of ASD (sensitivity to light, visual fixations, poor eye contact, etc.) as reported by parents and/or observed on videos taken during assessment.

Exclusion Criteria

- Known history of latex allergy
- Score 84 or below on the *Test of Nonverbal Intelligence- 4* (TONI-4; Brown, Sherbenou & Johnsen, 2009)
- Fail the hearing screening

Ethical Considerations

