Eliciting and Reporting Adverse Events: Subjects will be assessed for the occurrence of adverse events at each study visit. All adverse events occurring during the course of the study will be recorded on the Adverse Event Case Report Form and reported in accordance with the applicable regulations.

Identification of Adverse Events: An adverse event is defined as any new medical problem, or exacerbation of an existing problem, experienced by a subject while enrolled in the study, whether or not it is considered device-related by the investigator.

Relationship of Adverse Events to the investigational Device: The study physician will assess the relationship of the adverse event to the investigational device. The relationship will be assessed using the following categories:

- **Definitely Related:** A direct cause and effect relationship between the investigational device and the adverse event exists.
- **Possibly Related:** A direct cause and effect relationship between the investigational device and the adverse event has not been clearly demonstrated, but is likely or very likely.

TITLE: The Effects of *ProFoveate*™ on Reducing Self- Stimulating Behaviors In Children Diagnosed With Autism Spectrum Disorders.

PI: [name]

Co-I: [name]

- Unlikely Related: A direct cause and effect relationship between the investigational device and the adverse event is improbable, but not impossible.
- Unrelated: The adverse event is definitely not associated with the investigational device.

Serious Adverse Events: Each adverse event will be assessed for its seriousness using the criteria outlined below. The term serious adverse event is not synonymous with a “severe” adverse event, which may be used to describe the intensity of an event experience by the subject. An adverse event will be classified as serious if it meets any of the following criteria:

- Results in, or contributes to, a death;
- Life-threatening (i.e., the subject was, in the opinion of the investigator, at risk of death at the time of the event, but it does not include an event that, had it occurred in a more severe form, might have caused death);
- Results in permanent disability or incapacity (i.e., permanent impairment of a body function or permanent damage to a body structure);
- Requires in-patient hospitalization or prolongs hospitalization;
- Necessitates medical or surgical intervention to preclude a permanent disability or incapacity;

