- Results in a congenital anomaly or birth defect.

Non-serious adverse events are all events that do not meet the criteria for a “serious” adverse event.

Severity: Each adverse event will be assessed for its severity, or the intensity of an event experienced by the subject using the following:

- Mild: Discomfort noticed, but no disruption to daily activity.
- Moderate: Discomfort sufficient to reduce or affect normal daily activity.
- Severe: Inability to work or perform normal daily activity.

Deaths: The investigator will notify the Sponsor as soon as possible, preferably within 24 hours but in no event later than 48 hours, of learning of a subject’s death, regardless of whether the death is related or unrelated to the investigational drug. The investigator will attempt to determine, as conclusively as possible, whether the death is related to the device. The cause of death and the investigator’s discussion regarding whether or not the death was device-related will be described in a written report.

Pre-existing Conditions: Pre-existing conditions will not be reported as an adverse event unless there has been a substantial increase in the severity or frequency of the problem which has not been attributed to natural history.

Unanticipated Adverse Device Effects: An unanticipated adverse device effect is defined as any serious adverse effect on health or safety, or any life-threatening problem, or death caused by, or associated with, a device; if that effect, problem, or death was not previously identified in nature, severity, or degree of incidence in the investigational plan, or application (including supplementary application), or any other unanticipated serious problem associated with a device that relates to the rights, safety, or welfare of subjects.

If an unanticipated adverse effect occurs, the investigator will promptly notify the sponsor of such an event within 24 hours of first learning of the event. The investigator will notify the IRB of such an event as soon as possible, but no later than ten (10) working days after first learning of the event.

Statistical Plan

TITLE: The Effects of *ProFoveate*™ on Reducing Self- Stimulating Behaviors In Children Diagnosed With Autism Spectrum Disorders.
PI: [name]
Co-I: [name]

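### The pre-existing-condition rule withholds worsening that the adverse event definition counts, so some device-provoked ear pulling, scratching or self-injury can go unrecorded

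*Protocol*

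**What the plan says.** The protocol's Safety Assessments section contains three statements that bear on a worsened baseline problem.

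- **Identification of Adverse Events** defines an adverse event as "any new medical problem, or exacerbation of an existing problem, experienced by a subject while enrolled in the study", and adds "whether or not it is considered device-related by the investigator".
- **Eliciting and Reporting Adverse Events** says: "All adverse events occurring during the course of the study will be recorded on the Adverse Event Case Report Form".
- **Pre-existing Conditions** keeps such conditions out of adverse event reporting "unless there has been a substantial increase in the severity or frequency of the problem which has not been attributed to natural history".

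Other sections show which baseline problems are likely.

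- **Inclusion Criteria** allow a child to qualify through noticeable self-stimulating or ritualistic "behaviors (i.e., scratching, hand flapping, eye blinks, etc". Visual characteristics of autism are the and/or alternative.
- **Study Design and Procedures** lists twenty-five target behaviours. They include scratching, pulling or twisting the ear, and "vocal noises, mouthing, self-injurious behaviors, head banging".
- **Study Treatment Instructions** place the pellets on the right ear.
- **Risks Associated with ProFoveate** names abrasion as a possible effect.

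**The concern.** In many trials a clause on pre-existing conditions touches only incidental complaints. Here the baseline problems are the study's target, and several of them are plausible reactions to an adhesive patch on the ear: scratching it, pulling it or, in some children, self-injury. A child who already scratches and begins to scratch more under the patch has an exacerbation of an existing problem. A site following the pre-existing-condition paragraph could leave that off the adverse event form, either because the rise was not judged substantial or because it was put down to the course of autism.

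An event left off the form does not reach the study physician, who is the person assigned to judge whether the device was responsible. In a study of whether the device lowers these behaviours, a provoked rise is among the harms a reader would most want to see.

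**Working it through.** No arithmetic applies, and the protocol offers no figure to reproduce. The check sets the rules side by side.

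**Conditions for counting a worsened existing problem**

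| | Adverse event definition and recording rule | Pre-existing-condition rule |
|---|---|---|
| Size of worsening | No threshold | Must be substantial; term not defined |
| Cause | Counts whether or not considered device-related | Must not have been attributed to natural history; no assessor or criterion named |

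**Outcome by type of worsening**

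| Worsening of a pre-existing problem | Under the definition | Under the pre-existing-condition rule |
|---|---|---|
| (a) Less than substantial | Adverse event | Not reported |
| (b) Substantial, attributed to natural history | Adverse event | Not reported |
| (c) Substantial, not so attributed | Adverse event | Reported |

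The rules conflict in (a) and (b) and agree only in (c). The severity scale in the same section begins at a mild grade, meaning discomfort without disruption of daily activity. Small events were therefore meant to be within scope, which makes the silent threshold in (a) harder to reconcile.

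**Order of judgement.** The study physician rates the relationship of an adverse event to the device. In case (b), a judgement about cause has already been made before there is any adverse event to rate.

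**Do the outcome data fill the gap?**

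1. Video is taken at Visits 1 and 3. The patch is worn on days 2-29, and Visit 3 falls on days 30-34 after treatment has stopped. The ratings therefore do not observe behaviour while the patch is on.
2. The parent questionnaire is given at the same two visits and analysed as a summed score before and after treatment. It may reflect what parents recall of the wearing period, but it is an efficacy score.
3. The diary instructions concern checks of pellet placement.

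None of these sources is described as passing to the study physician for a relatedness rating.

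**The case against.** The best defence is that a specific clause following a general definition may be read as explaining when a pre-existing condition counts as exacerbated. The definition sets aside only device-relatedness, and natural history is a different test, so the definition does not in terms forbid the attribution. Worsening truly provoked by the device is not natural history and, if substantial and correctly judged, is reported. A new wound, rash or abrasion is a new medical problem and is unaffected. Unanticipated serious device effects have their own notification route.

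Much of this stands, and it limits the point to cases (a) and (b). It does not remove the conflict. The text does not present the later clause as a narrowing, and the earlier statements say any and all. Natural history is a different test from device-relatedness, but attributing worsening to it settles the cause before the person assigned to judge relatedness sees the event.

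Several stronger readings are tempting, and the protocol does not support them.

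- **Harms are filtered by unblinded judgement.** The Statistical Plan calls the parent ratings unblinded, and the PI is blinded during the ERP procedure. Nothing says who makes the natural-history attribution or whether that person knows the group.
- **A comparison of adverse events between arms is biased.** No such analysis is described, and adverse events are not among the seven dependent variables. Adverse Event Review applies to both groups, so directional bias would need attribution to differ by group, which is not shown.
- **The rule affects up to all 30 children.** Children may qualify on visual characteristics alone, and only 15 are assigned to wear the device.
- **A rise in self-injury or head banging would be offset by falls in the other 23 of the 25 behaviours.** The questionnaire's item structure is in materials not shown.

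**Conclusion.** The conflict is real and holds on the wording alone. If the pre-existing-condition paragraph is followed, some worsening during treatment that the definition counts will not be recorded as an adverse event or rated for relatedness. It covers worsening that is less than substantial and substantial worsening attributed to natural history, in children who enter with the behaviour concerned. It does not hide all device-provoked harm.

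The size cannot be estimated. The protocol gives no baseline frequency of ear pulling, scratching or self-injury and no expected event rate. Device-provoked worsening is possible in at most the 15 children assigned to the device, and the number of those with a relevant baseline behaviour is unknown.

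The conclusion rests on one assumption: that not reporting a condition as an adverse event also keeps it off the adverse event form. That is the natural reading, since the form is where adverse events are recorded, but the protocol does not say so outright.

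A reader might also infer that every increase in a pre-existing problem should be recorded. That goes further than is needed. The target behaviours may fluctuate, and logging each rise would largely duplicate the efficacy outcome. The change is worth making, but the point does not call the design into question.

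**What to change.** Reconcile the Pre-existing Conditions paragraph with the adverse event definition as follows.

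1. Remove the attribution to natural history as a condition for recording.
2. State that worsening from Visit 1 of a listed behaviour is recorded in both arms when it causes injury or is directed at the ear.
3. State that the study physician's relatedness rating is made after the event has been recorded.
4. If a size threshold is kept for other pre-existing problems, define it and refer to it in the adverse event definition, so that the two paragraphs give the same answer.

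The change is to protocol wording on event recording. No visit, assessment or treatment procedure changes. The cost is some additional non-serious entries in both arms; the protocol gives no basis for estimating how many.

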1. Are there differences between the HFASD experimental and HFASD control group in the occurrence of self-stimulating behaviors as reported by caregivers, following *ProFoveate™* intervention?
2. Are there differences between the HFASD experimental and HFASD control group in social interaction skills as reported by caregivers, following *ProFoveate™* intervention?
3. Are there electrophysiological changes in the brains of individuals with HFASD in the control group compared to HFASD individuals in the experimental group, as measured by EEGs following *ProFoveate™* intervention?

The long term goal of this line of research is to determine if the supposition that the *ProFoveate™* intervention is beneficial to children with HFASD is substantiated by evidence from parent report of changes in self-stimulating behaviors and social interaction skills as well as by measures of change in neural activity in the experimental group. The first step in this process is to conduct a pilot study. Depending on the findings of this pilot study, future studies may be conducted with modifications to the procedures and more participants.

Test Article

Investigational Device

ProFoveate™ intervention for nystagmus is a management approach comprised of non-magnetic, 1.2 mm spheres that can be made from either stainless steel, gold or silver plated stainless steel or titanium, placed strategically about the face and ears and a set of exercises designed to support improved vision for patients with nystagmus. The spheres chosen for this study will be five pellet patches. We decided to use five pellet patches to ensure proper placement on the occiput with our target minor population. These multi pellet patches are 0.5" x 0.5" adhesive plasters that contain latex. Each patch features a geometrically spaced cluster of five 1.2 mm silver plated pellets. They are available from Lhasa OMS at <http://www.lhasaoms.com/> and come in packet of 50 pellets. We will give each participant one packet of 50 five pellet patches which will be enough for the study time frame. Any unused pellets will be returned. Individual patches (with adhesive tape) are removed from the backing as needed according to the prescribed treatment regimen. (See Figure 1)

Figure 1: *ProFoveate Five Pellet Patches* <http://www.lhasaoms.com/>

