This is a pilot study aimed at examining the effects of *ProFoveate*™ intervention on reducing some of the hallmark characteristics of HFASD. Specifically, we are interested in documenting any changes in self-stimulating behaviors or social skills and neural activity as reported by parents and EEGs. A two group control group design will be utilized where both the experimental group and control group of individuals with HFASD will receive assessments of self- stimulating behaviors, social skills and neural activity at baseline. The experimental group will receive the *ProFoveate*™ intervention followed by reassessment of both the experimental and control groups at the end of the study. The target participants are 30 children diagnosed with HFASD between the ages of 10 and 17 years and their parents. This older age group was chosen because the participants must able to apply and monitor the *ProFoveate*™ pellets. Participants will be recruited by sending out flyers (See Flyer attachment) to autism support groups and to previous clients of a social skills program at the UALR Speech and Hearing Clinic. Participants who are interested in participating will make an appointment. At that time the consent form will be reviewed and any questions will be answered by the principal investigator. Participants will be given as much time as needed to review the consent/assent forms (See consent and assent form attachments). Those who provide consent/assent and have a documented diagnosis of ASD (autism, Asperger's syndrome, or PDD-NOS) will be assessed. Participants will come to the UALR Speech and Hearing Clinic for four visits. Visit

TITLE: The Effects of *ProFoveate*™ on Reducing Self- Stimulating Behaviors In Children Diagnosed With Autism Spectrum Disorders.

PI: [name]

Co-I: [name]

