
pressing task that provides the accuracy of their responses and reaction time. Following EEG recordings, ERP analysis time windows will be set *post hoc* permitting a -100 ms pre-stimulus baseline and a post-stimulus time that extends well beyond the P300 latency (e.g., epoch of -100 to 700 ms). EEGs will undergo ocular artifact rejection and be baseline corrected prior to production of an average to all target stimuli. P300 amplitude and latency measures will also be taken. These procedures are expected to last no more than one to one and a half hours in a single session or a split session depending on the needs of the participant. During the administration of ERP procedure, the PI will not be aware if the child participant undergoing the procedure is in the control group or experimental group. This approach will support internal validity and minimize the potential for investigator bias. Sample waveforms showing several ERP components, including [P300](#) are presented in Figures 4.

[figure not shown]

Figure 4: <http://en.wikipedia.org/wiki/File:ComponentsofERP.svg>

Following initial assessment, child participants will be randomly assigned to either the control group (15 participants) or the experimental group (15 participants). Participants in the experimental group will be required to wear the *ProFoveate*™ metal pellets held in place by small adhesive bandages strategically placed on their ears during days 2-29. Participants in the experimental will be told to return for the final assessment on days 30-34 following cessation of treatment. Participants in the control group will receive no study intervention. Participants in the control group will be told to return for final assessment on days 30-34 following initial assessment.

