To determine significance in the occurrence of self-stimulating behaviors or social skills following *ProFoveate*™ intervention nonparametric statistics will be run on questionnaire and test data obtained from the experimental and control groups. Test data will consist of pre and post treatment standard scores obtained from the test manuals and questionnaire data will consist of pre and post treatment summative Likert scores reported by parents. In order to gather ERP data, use of the STIM² software, SCAN EEG analysis software and associated hardware/peripheral devices (located in the Auditory Electrophysiological (Re)Habilitation Lab of the PI) for data gathering and analysis of the P300 ERP will be utilized for each participant. There are two independent variables: control group and experimental group. There are seven dependent variables: SSIS parent scores, SSIS student scores, TOPL-2 scores, blinded P50 measures, blinded P300 measures, Parent Questionnaire scores and blinded video ratings of self-stimulating behaviors (see supporting materials). Interjudge reliability for video ratings will be established by having two observers review 25% (8) of the video recordings, document the occurrence of self-stimulating behaviors and calculating the percent agreement. These scores will be triangulated to compensate for the fact that the parent ratings are not blinded. The data will be analyzed using a 2 (group) x 3 (standardized scores) x 1 (Physiological measure) x 2 (observational measures) repeated measures multivariate analysis of variance (See Figure 5).

Data Handling and Recordkeeping

All questionnaires and test forms will be maintained by the principal investigator in a locked file accessible only to the staff of the research study for three years. Both assessment sessions with students will be video recorded for later analysis of observable self- stimulating behaviors. Only the co-investigator and Citi-certified graduate students will view the videotapes. The videotapes and assessment protocols will be maintained in a locked file in the co-investigator's lab for three years and then destroyed.

Confidentiality

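### Neither analysis in the Statistical Plan adjusts the final score for its own baseline, and the written layout does not fix which between-group contrast is tested

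*Protocol*

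**What the plan says.** Under Study Design and Procedures, both groups "will receive assessments of self- stimulating behaviors, social skills and neural activity at baseline" and are reassessed at the end. The Schedule of Time and Events lists the SSIS student and parent forms, TOPL-2, parent questionnaire, video recording and EEG once before and once after the intervention period. After the initial assessment, "child participants will be randomly assigned to either the control group (15 participants) or the experimental group (15 participants").

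The Statistical Plan brings both time points into the analysis. For the tests, "Test data will consist of pre and post treatment standard scores obtained from the test manuals". The parent questionnaire likewise enters as summed Likert ratings from both time points.

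It then names two analyses:
- "nonparametric statistics will be run on questionnaire and test data obtained from the experimental and control groups". No test is named, and the text does not say whether it compares final scores or changes.
- A "2 (group) x 3 (standardized scores) x 1 (Physiological measure) x 2 (observational measures) repeated measures multivariate analysis of variance". The layout lists group and types of measure. It lists no pre/post factor and no covariate.

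The first research question is a comparison between groups: "Are there differences between the HFASD experimental and HFASD control group in the occurrence of self-stimulating behaviors as reported by caregivers". The null hypothesis is worded as an absence of change after the intervention. The protocol states no alpha, power, SD, effect size or pre/post correlation.

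**The concern.** In a randomised trial with one baseline and one final measurement, there are three usual between-group contrasts: final score, change score, and final score adjusted for baseline (ANCOVA). The analyses named here would ordinarily test one of the first two. ANCOVA is at least as precise as either in large samples. It is also the only one of the three that allows correctly for a baseline difference that has arisen by chance.

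With 15 children per arm, such differences are common and precision is short. This is a pilot whose findings are meant to decide whether and how further studies follow, so an estimate shifted by a chance imbalance would carry forward. Because the contrast is not fixed in writing, it could also be chosen once the data are seen.

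**Working it through.** **Inputs from the protocol.** 15 per arm; baseline and final measurement of the outcomes; no baseline covariate. The plan gives no precision or power figure to reproduce.

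**Assumptions.** Two-sided 5% test, 80% power, equal SD of 1 at both times, no dropout, pre/post correlation r = 0.5, 0.7 or 0.8.

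**1. What a group-by-time test is.** With two time points, the repeated measures group-by-time F equals the squared t statistic on change scores. On one simulated data set both were 0.3219. If the MANOVA includes time, its group-by-time contrast is therefore a change-score analysis.

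**2. Chance imbalance.** The SD of the baseline difference is √(2/15) = 0.365 SD. A difference of 0.5 SD is 0.5/0.365 = 1.37 standard errors, so P(|difference| > 0.5 SD) = 0.17 for a given outcome.

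**3. Effect of an imbalance D on the estimate.**
- Final score: shifted by r·D. With D = 0.5 SD, that is +0.25 SD at r = 0.5 and +0.40 SD at r = 0.8.
- Change score: shifted by (r − 1)·D, that is −0.25 SD at r = 0.5 and −0.10 SD at r = 0.8. The sign is reversed, which is over-correction.
- ANCOVA: about 0.

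**4. Variance relative to a final-score comparison.**
- Final score: 1.
- Change score: 2(1 − r).
- ANCOVA: (1 − r²) × 27/26. The factor is 1 + 1/(2n − 4) with n = 15, the cost of estimating the slope in a trial of this size.

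| r | Change | ANCOVA | ANCOVA/change | Reduction v change | Reduction v final |
|---|---|---|---|---|---|
| 0.5 | 1.00 | 0.75 × 27/26 = 0.779 | 0.779 | 22% | 22% |
| 0.7 | 0.60 | 0.51 × 27/26 = 0.530 | 0.883 | 12% | 47% |
| 0.8 | 0.40 | 0.36 × 27/26 = 0.374 | 0.935 | 6.5% | 63% |

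Against change scores, the reduction is like having 30/0.779 ≈ 38, 30/0.883 ≈ 34 or 30/0.935 ≈ 32 children instead of 30.

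**5. Detectable difference and power** (noncentral t; 28 df for final and change, 27 df for ANCOVA).

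| r | Detectable, final | Detectable, change | Detectable, ANCOVA | Power at 0.8 SD: final / change / ANCOVA |
|---|---|---|---|---|
| 0.5 | 1.06 | 1.06 | 0.94 | 56% / 56% / 67% |
| 0.7 | 1.06 | 0.82 | 0.77 | 56% / 78% / 83% |
| 0.8 | 1.06 | 0.67 | 0.65 | 56% / 92% / 93% |

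**6. The written layout taken literally.** If no time term is fitted and group is tested on the average of pre and post, the contrast estimates only half the effect, with SD √((1 + r)/2). For a true difference of 0.8 SD, power is about 24% at r = 0.5 and 22% at r = 0.7. A final-score test has 59% on the same normal approximation.

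**The case against.** The strongest reply is that the protocol leaves the test open rather than excluding adjustment. A rank-based ANCOVA could be called nonparametric, covariates are often left to an analysis plan that is not shown here, and the layout points to a Figure 5 that is not reproduced in the text. This stands in part: the figure may show a time factor, so only the written layout can be said to lack one. It does not remove the point. The protocol has its own Statistical Plan that names methods, and those methods as ordinarily run do not condition the final score on baseline.

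A reader might infer that the plan ignores baseline and leaves imbalance wholly uncorrected. The documents do not support that. Pre and post scores both enter, and the model is called repeated measures. If group by time is tested, baseline is used and an imbalance is over-corrected. Nor is either simple contrast biased over repeated randomisations; the shifts in step 3 are conditional on the imbalance that happens to occur.

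A reader might also apply the large-sample ratio (1 + r)/2, which gives reductions of 25%, 15% and 10% against change scores. That overstates the gain with 30 children. At high r the gain is small: at r = 0.9 the ratio is 0.95 × 27/26 = 0.987, about 1%.

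Finally, this is a pilot with no stated power target, so no stated goal is missed. That limits the severity, but the improvement remains nearly free.

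**Conclusion.** The point holds in a limited form. No stated analysis adjusts the final score for its baseline. The text names two conflicting approaches for the questionnaire and test scores, and its written layout does not fix the between-group contrast.

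The size depends on which contrast would be run. Against change scores the loss is modest, and nearly disappears when scores are highly stable over the month. Against final scores it is substantial. The figures rest on an assumed r of 0.5 to 0.8, equal SDs, complete data and roughly normal scores; none of these comes from the protocol. The 63% reduction should not be quoted as the plan's loss, because the protocol does not say that final scores alone are compared.

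The change is worth making because it improves on either ordinary contrast over this range and settles the ambiguity.

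**What to change.** In the Statistical Plan, replace the nonparametric tests and the MANOVA with one model per outcome: final score as response, group as factor, and that outcome's own baseline as covariate. Report the adjusted group difference with its 95% confidence interval. For Likert sums and video counts, keep the nonparametric intent with a rank ANCOVA or a permutation p-value for the group term.

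The EEG baseline falls at Visit 2, after randomisation and at the visit when pellets are dispensed. The text should therefore state that the value used as covariate is recorded before the first application.

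The cost is a rewording of one section and one degree of freedom per model. No new data, visits or children are needed.
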